8.3 IHC Measurements

A minimum of 1 formalin-fixed paraffin-embedded (FFPE) tumor tissue block from pre-study surgery confirming GBM are to be submitted within 60 days of registration. Additionally, a minimum 1 formalin-fixed paraffin-embedded (FFPE) tumor tissue block (preferred) or a minimum of 10 FFPE unstained sections from the protocol surgery are to be submitted per Table 6 below. Archival tumor samples from the protocol surgery should be shipped to the UCLA Brain Tumor Research Lab. Multi-plex IHC stained will be performed to assess: 1) the proportion of PD-L1 expression on GFAP+ tumor cells versus myeloid cells (CD68+ or CD163+) within the tumor microenvironment and subsequently batch shipped to a central lab determined by Merck for determination of PD-L1 expression at the end of the study.

NOTE: archival tumor tissue from pre-study surgery and protocol surgery submitted to the DFCI Coordinating Center outside of protocol mentioned timelines will not be logged as a violation. Sites will be tracked for compliance, but IRB reporting of out of window submission will not be required.

8.4 Gene expression signatures and somatic mutations

Tumor samples from the protocol surgery should be immersed in Allprotect tissue reagent solution (Qiagen) or RNA-later® reagent and shipped to the UCLA Brain Tumor Research Laboratory. RNA Seq will be performed at the UCLA GenoSeq Core facility and analyzed. We will assess the number of somatic mutations in each tumor and this data will be correlated with clinical variables to identify potential biomarkers with prognostic and predictive value for outcomes (ORR, PFS, OS). We will also develop immune signatures with the sequencing data and evaluate whether the presence of a pre-existing immune signature can also be correlated with clinical variables.

8.5 Sample Shipping Instructions & Details to UCLA

Guidelines for submission of archival tumor tissue (FFPE), fresh-preserved tumor tissue, and/or whole blood (please see Table 6 below for details):

- A memorandum indicating the study, the date of submission, name of study site submitting the tissue, and a list of contents. The DFCI Neuro-Oncology Coordinating Center or UCLA Brain Tumor Research lab will supply a template memorandum to sites at the time of the SIV or upon request.
- The DFCI Neuro-Oncology Coordinating Center will provide supplemental 16-225 Sample Collection & Shipping Guidance to sites at the time of activation or upon request.
- A copy of the pathology and surgical report for the sample being submitted should be included in the shipment.
- Slides should be shipped in a plastic slide holder/slide box. Place a small wad of padding in top of the container in order to avoid slides breaking during shipping and handling process.
- All blood & tissue samples addressed to UCLA should be shipped via FedEx for overnight

delivery. On-study tissue & blood samples should be obtained Sunday-Thursday for a Monday-Friday arrival at UCLA. **UCLA is unable to accept samples on Saturday or Sundays.**

- An email should be sent before or at the time of each shipment to the UCLA Brain Tumor Research lab below or the DFCI Neuro Oncology Coordinating Center at [contact] (or the designated Coordinating Center Project Manager) indicating what is being shipped and when.

- Please note that the submitting institution is responsible for the costs of shipping and handling.

- Ship samples to:

[name].
C/O [name]
[name]
[name]
Los Angeles, CA 90095
[contact]
Email: [contact] and [contact]

TABLE 6 CORRELATIVE SAMPLE SUMMARY
Table 6 Continued on next page

Biomarker name (Lead PI and Site)	Assay	Tissue/Body Fluid Tested and Timing of Assay	Collection and packaging	Address to send sample
TIL Density and TCR Overlap ([name]/[name]/[name], UCLA)	TCR ImmunoSeq and TCR Overlay (Adaptive Biotech.) on tumor tissue and peripheral blood mononuclear cell genomic DNA	Tumor (protocol surgery) and peripheral blood (Pre-Tx, Post-Tx)	200 mg of fresh tissue (approximately 20% tumor nuclei) sent in 2 mL Allprotect ® tissue reagent (Qiagen) or RNA-later® reagent Pre-treatment and post-treatment PBMC can be used from blood collected for flow cytometry (see below)	[name]. C/O [name] [name] [name] Los Angeles, CA 90095 [contact] Email: [contact] and [contact]
IHC measurements ([name]/[name]/[name], UCLA)	PD-1/PD-L1/CD8/CD4/CD8/Iba-1/CD68/GFAP IHC on FFPE tumor tissue	Archived and protocol surgery from tumor block	Archived: 1 formalin-fixed paraffin embedded (FFPE) tumor tissue block (preferred) from most recent surgery revealing glioblastoma Protocol Surgery: 1 FFPE tumor tissue block (preferred) or a minimum of 10 FFPE unstained sections	[name]. C/O [name] [name] [name] Los Angeles, CA 90095 [contact] Email: [contact] and [contact]
Peripheral blood T cell subsets/activation markers ([name]/[name]/[name], UCLA)	Flow Cytometry on peripheral blood mononuclear cells	Peripheral blood (Pre-surgery pre-treatment, pre-surgery post treatment, with every MRI)	Pre-surgery pre treatment blood (for Groups A and B) : 10 Green top tubes (10ml/tube – sodium heparin tubes preferred) following registration/randomization and pre-pembrolizumab for Group A Pre-surgery, day 7 post pembrolizumab administration (+/- 2 days): 10 Green top tubes 10-ml sodium heparin tubes preferred (should not be same timepoint as next 'pre-surgery post treatment' blood) Pre-surgery: 10 Green top tubes 10ml – sodium heparin tubes preferred (should be greater than 10 days from initial dose of Pembrolizumab for Group A – Group B should also have a sample drawn pre-surgery, greater than 10 days from initial sample)	[name]. C/O [name] [name] [name] Los Angeles, CA 90095 [contact] Email: [contact] and [contact]
Gene expression signatures and somatic mutations ([name] / [name] / [name])	RNA Seq on tumor RNA	Tumor (protocol surgery) and peripheral blood	Blood with each MRI (- 7 days before next cycle pembrolizumab infusion): 10 Green top tubes 10ml – sodium heparin tubes preferred	[name]. C/O [name] [name] [name] Los Angeles, CA 90095 [contact] Email: [contact] and [contact]

TABLE 6 CORRELATIVE SAMPLE SUMMARY (CONT'D)

Biomarker name (Lead PI and Site)	Assay	Tissue/Body Fluid Tested and Timing of Assay	Collection and packaging	Address to send sample
Tumor mRNA from extracellular vesicles ([name], Institute for Systems Biology / [name] Lab - processing)	Liquid biopsy of a partial tumor transcriptome	EDTA plasma (Pre-surgery pre-treatment, pre-surgery post treatment, with every MRI)	Pre-surgery pre-treatment blood: 2-10ml K2EDTA tubes following registration/randomization and pre-pembrolizumab Pre-surgery: 2-10ml K2EDTA tubes same day or -1 day from on-study surgery Blood with each MRI (- 7 days before next cycle pembrolizumab infusion): 2-10ml K2EDTA tubes Blood with each MRI (- 7 days before next cycle pembrolizumab infusion): 2-10ml K2EDTA tubes	[name]. C/O [name] [name] [name] Los Angeles, CA 90095 [contact] Email: [contact] and [contact]

9. STUDY CALENDAR

Screening/baseline evaluations are to be conducted within 14 days of registration unless indicated otherwise. Assessments must be performed and reviewed prior to administration of any study agent at any treatment visit unless otherwise noted in footnotes below. Study assessments should be performed and study drug should be administered within +3/-3 days of the protocol-specified date, unless otherwise noted.

Assessments	Screening ^a		Pre-Surgery ^b	Pre-Surgery Day 7 ^{ff}	Surgery	Post-Surgery	Post-Surgery Treatment Cycles D1 ^b D22 ^c		End of Tx ^d	30-Day Post Drug ^e	Active Follow Up ^f	Long Term Follow Up ^g
	Pre-Surgery	Day 7 ^{ff}					D1 ^b	D22 ^c				
Informed Consent ^h	X											
Background Information/History ⁱ	X											
Inclusion/Exclusion Criteria ^j	X											
Vital Signs ^k	X	X					X	X	X	X	X	
Neurologic Exam ^l	X	X					X	X	X	X	X	
Directed Physical Exam ^m	X	X					X	X	X	X	X	
Karnofsky Performance Status ⁿ	X	X					X	X	X	X	X	
Concomitant Medications ^o	X											
Adverse Event Assessment ^p												
Pregnancy Test – Urine or Serum β-HCG ^q	X						X			X	X	
Coagulation ^r	X											
Hematology ^s	X	X					X	X	X	X	X	
Serum Chemistry ^t	X	X					X	X	X	X	X	
T3, FT4, TSH ^u	X	X					X	X	X	X	X	
Imaging – CT or MRI ^v	X						X ^{v,ee}	X ^v	X	X	X	
Response Assessment ^w							X ^x	X ^x	X	X	X	
Pembrolizumab Administration ^x		X ^x										
Blood for Flow Cytometry ^z	X											
Blood for tumor mRNA ^y	X											
Tumor Resection ^{aa}												
Submission of Archival Tissue ^{bb}	X											
Post-End-of-Treatment Therapies ^{cc}										X	X	X
Survival ^{dd}										X	X	X

- a. All screening procedures to be performed within 14 days of registration, except informed consent may occur up to 28 days prior to registration.
- b. Pre-Surgery Day 1 and Day 1 of subsequent cycles: For Pre-Surgery Day 1 only, screening assessments may serve as day 1 assessments, except in the event that there are any indications that the participant's condition is deteriorating for which laboratory evaluations should be repeated within 48 hours prior to initiation of on-study assessments. For all subsequent cycles (post-surgery), required assessments should be performed within 3 days of scheduled cycle day 1.
- c. Day 22 window requirements: pembrolizumab must be administered $+/- 3$ days from Day 22 of each cycle. Assessments must be performed and reviewed prior to study agent administration.
- d. End of Tx: End of treatment assessments to be performed within 7 days after last drug administration or within 7 days after decision to end treatment. Assessments may continue for ongoing reportable adverse events.
- e. 30-Day Post Drug: A contact/visit is to be performed at 30 days ($+ 7$ days) after the last study drug is given. This may be performed via documented phone conversation with a study nurse or clinician or a clinic visit. All participants will be followed until resolution or stabilization of any serious or reportable adverse events occurring during treatment or starting within 30 days of last study drug.
- f. Active Follow Up: For participants who discontinue study treatment for reasons other than disease progression, every effort should be made to continue monitoring their disease status by radiologic imaging at a schedule developed by the treating investigator until (1) documented disease progression, (2) death or (3) the end of the study, whichever occurs first.
- g. Long Term Follow Up: participants will be followed every 3 months ($+/- 1$ month) via contact or medical record review until death for post-treatment therapies, reason for stopping those therapies and survival.
- h. Informed Consent: Must be obtained by MD attending. No study specific screening procedures may occur until after the informed consent process is complete. Informed Consent may be obtained within 28 days of registration.
- i. Background information/history: to include review of treatment history for GBM, any ongoing medical conditions and medical history pertaining to eligibility on study and involvement during study.
- j. Inclusion/exclusion criteria: source documentation providing investigator's confirmation that the participant had met all eligibility criteria must be available prior to registration.
- k. Vital signs: weight, heart rate, blood pressure, respiration rate, temperature. Vital signs must be performed prior to administration of treatment on treatment days. Height required only at screening and may be obtained within 1 year of registration.
- l. Neurologic Exam: to be completed by the investigator or qualified designee at screening, C1D1 and start of all subsequent cycles.
- m. Directed Physical Exam: to be completed as clinically indicated by the investigator or qualified designee.
- n. Performance Status: See Appendix A for KPS scale.
- o. Concomitant medications: concomitant medications and reason for administration should be documented in the case history from date of consent up to the 30-Day Post Drug Visit. Concomitant medications administered after 30 days after the last dose of trial treatment should be recorded for SAEs and ECIs.
- p. Adverse event assessment: adverse events experienced by participants will be collected and recorded from registration to the 30-Day Post Drug Visit of the last dose of study medication ($+ 7$ days depending on when 30-Day Post Drug visit/contact occurs) and all SAEs (related and unrelated to trial treatment) / ECIs up to 90 days after the last dose of trial treatment or the start of new anti-cancer treatment, whichever comes first. Afterwards, report only SAEs and ECIs that are considered related to trial treatment. Adverse events may also occur in screened subjects during pre-allocation baseline period as a result of a protocol-specific intervention, including washout or discontinuation of usual therapy, diet, placebo treatment or a procedure.
- q. Pregnancy Test: For women of child bearing potential, a pregnancy test must be performed. If urine pregnancy results cannot be confirmed as negative, a serum pregnancy test will be required.
- r. Coagulation: PT/INR, PT, PTT required at screening only and then as clinically indicated.
- s. Hematology: erythrocytes (RBC), hemoglobin, hematocrit, platelets, total WBC plus differential (neutrophils, lymphocytes, monocytes, eosinophils, basophils).
- t. Serum Chemistry: albumin, alkaline phosphatase (ALP), bicarbonate (HCO_3) or CO_2 , BUN, calcium, chloride, creatinine, glucose, magnesium, potassium, SGOT (AST), SGPT (ALT), sodium, total protein, total bilirubin.

- u. T3,FT4, TSH: total triiodothyronine (T3), free thyroxine (T4), and thyroid stimulating hormone (TSH). T3, FT4, TSH must be drawn prior to pembrolizumab administration; if results are not available for review prior to pembrolizumab administration, study treatment may proceed. Results should be reviewed when they become available.
- v. Imaging: gadolinium-enhanced contrast and non-contrast MRI. CT alternative, if MRI contraindicated. Initial imaging should be performed within 14 days prior to registration. On-study imaging should be performed every 6 weeks at Day 1 of each cycle (-7 days). The same imaging technique should be used in a participant throughout the trial, if feasible. Local reading (investigator assessment) will be used to determine eligibility and for participant management.
- w. Response Assessment: Per RANO criteria (section 10).
- x. Pembrolizumab Administration: Pre-surgery pembrolizumab required for participants randomized to Group A only (14 days +/- 5 days prior to day of surgery). Post-surgery pembrolizumab must start no more than 35 days following surgery. Post surgery pembrolizumab may be administered +/- 3 days from days 1 and 22 of each cycle.
- y. Blood for tumor mRNA: please see Table 6 Correlative Sample Summary for details on collection requirements.
- z. Blood for Flow Cytometry: please see Table 6 Correlative Sample Summary for details on collection requirements.
- aa. Tumor Resection: please see Table 6 Correlative Sample Summary for details on collection requirements. On-study surgery tissue should be submitted within 60 days of surgery.
- bb. Submission of archival tissue: archival tumor tissue should be submitted within 60 days of registration. Please see section 8.3 for details.
- cc. Post-end-of-treatment oncology therapies: start/stop dates, names of treatment regimens and reason for stopping should be collected.
- dd. Survival: date of death and reason should be collected for overall survival purposes, when applicable.
- ee. For post-surgery MRI (for both Group A and B participants), if the post-surgery MRI is greater than 21 days from post-surgery pembrolizumab initiation, then MRI must be repeated.
- ff. Blood for Flow Cytometry (added in Stage 2) must be drawn 7 days after initial pembrolizumab administration (+/- 2 days). Please see Table 6 Correlative Sample Summary for details on collection requirements.

10. MEASUREMENT OF EFFECT

Tumor response will be assessed every 6 weeks for patients treated on this study using RANO criteria¹⁰⁴ as outlined below. Clinicians may repeat response assessment more frequently as clinically indicated.

10.1 Anti-Tumor Effect Definitions

10.1.1 Evaluable for toxicity. All participants who receive at least one dose of study treatment will be evaluable for toxicity from the time of their first treatment.

10.1.2 Evaluable for objective response. Only those participants who have measurable disease present at baseline (obtained within 14 days of cycle 1, day 1) scan and have received at least one dose of therapy will be considered evaluable for response. These participants will have their response classified according to the definitions stated below. (Note: Participants who exhibit objective disease progression or die prior to the end of cycle 1 will also be considered evaluable.)

10.1.3 Measurable disease. Bi-dimensionally, contrast-enhancing, measurable lesions with clearly defined margins by CT or MRI scan, with a minimal diameter of 1 cm, and visible on 2 axial slices which are at least 5 mm apart with 0 mm skip. Measurement of tumor around a cyst or surgical cavity, if necessary, requires a minimum thickness of 3 mm. If there are too many measurable lesions to measure at each evaluation, the investigator must choose the largest two to be followed before a participant is entered on study. The remaining lesions will be considered non-measurable for the purpose of objective response determination. Unless progression is observed, objective response can only be determined when all measurable and non-measurable lesions are assessed.

10.1.4 Non-measurable evaluable disease. Unidimensionally measurable lesions, masses with margins not clearly defined, lesions with maximal diameter < 1cm.

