Group B: adjuvant evaluation: Fifteen eligible patients will not receive study drug prior to scheduled surgical resection for recurrent/progressive glioblastoma. The two required pre-surgical plasma samples should be drawn greater than 10 days apart - see Table 6 for full details). Tumor samples will be obtained at time of surgery. The tissue from this surgery (fresh, frozen and FFPE) and the archived tissue from the most recent surgery prior to registration revealing glioblastoma (FFPE) will be processed so as to best achieve the primary, secondary and exploratory PD objectives. After recovery from surgery (once participant has recovered from surgery, but no more than 35 days following surgery), patients will begin Q 3 week pembrolizumab at 200mg IV until tumor progression or adverse event requiring discontinuation of study drug. Blood samples will be obtained as pharmacodynamic markers throughout the study. Dose decreases and symptomatic management will occur based upon preset adverse event determination. DLTs will not be determined. The toxicity evaluation period will begin with registration and extend to 30 days after last treatment day. Patients will be followed for MRI changes, clinical exam and steroid doses from the registration period and extend to the second progression. After second progression, patients will be followed every 3 months for vital status until death.

Stage 2:

Group A expansion only: For this stage of the study, 25 additional patients will be enrolled to Group A only with a goal of 20 evaluable patients.

Expansion of Group A: Neoadjuvant/adjuvant evaluation: An additional 20-25 patients will receive a single infusion of pembrolizumab of 200mg 14± 5 days prior to scheduled surgical resection for recurrent/progressive glioblastoma (when scheduling, please keep in mind that the two pre-surgical plasma samples should be drawn greater than 10 days apart - see Table 6 for full details). Tumor samples will be obtained at time of surgery. The tissue from this surgery (fresh, frozen and FFPE) and the archived tissue from the archived tissue from the most recent surgery prior to registration revealing glioblastoma (FFPE) will be processed so as to best achieve the primary, secondary and exploratory PD objectives. After recovery from surgery (once participant has recovered from surgery, but no more than 35 days following surgery), patients will resume Q 3 week pembrolizumab at 200mg IV until tumor progression or adverse

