6. ADVERSE EVENTS: LIST AND REPORTING REQUIREMENTS

An adverse event is defined as any untoward medical occurrence in a patient or clinical investigation subject administered a pharmaceutical product and which does not necessarily have to have a causal relationship with this treatment. An adverse event can therefore be any unfavorable and unintended sign (including an abnormal laboratory finding, for example), symptom, or disease temporally associated with the use of a medicinal product or protocol-specified procedure, whether or not considered related to the medicinal product or protocol-specified procedure. Any worsening (i.e., any clinically significant adverse change in frequency and/or intensity) of a preexisting condition that is temporally associated with the use of the Merck's product, is also an adverse event.

Changes resulting from normal growth and development that do not vary significantly in frequency or severity from expected levels are not to be considered adverse events. Examples of this may include, but are not limited to onset of menses or menopause occurring at a physiologically appropriate time.

Merck product includes any pharmaceutical product, biological product, device, diagnostic agent or protocol-specified procedure, whether investigational (including placebo or active comparator medication) or marketed, manufactured by, licensed by, provided by or distributed by Merck for human use.

Adverse events may occur during the course of the use of Merck product in clinical trials or within the follow-up period specified by the protocol, or prescribed in clinical practice, from overdose (whether accidental or intentional), from abuse and from withdrawal.

Adverse events may also occur in screened subjects during any pre-allocation baseline period as a

result of a protocol-specified intervention, including washout or discontinuation of usual therapy, diet, placebo treatment or a procedure.

Progression of the cancer under study is not considered an adverse event.

All adverse events will be recorded from registration through 30 days following cessation of treatment and at each examination on the Adverse Event case report forms/worksheets. The reporting timeframe for adverse events meeting any serious criteria is described in section 6.3.

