6.3 Immediate Reporting of Adverse Events to the Sponsor and to Merck

6.3.1 Serious Adverse Events

A serious adverse event is any adverse event occurring at any dose or during any use of Merck's product that:

- Results in death;
- Is life threatening;
- Results in persistent or significant disability/incapacity;
- Results in or prolongs an existing inpatient hospitalization;
- Is a congenital anomaly/birth defect;
- Is a new cancer (that is not a condition of the study);
- Is associated with an overdose;
- Is another important medical event

Refer to Table 5 for additional details regarding each of the above criteria.

Progression of the cancer under study is not considered an adverse event unless it results in hospitalization or death. See section 6.3.1.5 Protocol Specific Expedited Adverse Event Reporting Exclusions for other events not requiring expedited reporting.

Any serious adverse event, or follow up to a serious adverse event, including death due to any cause other than progression of the cancer under study that occurs to any subject from the time the consent is signed through 90 days following cessation of treatment, or the initiation of new anti-cancer therapy, whichever is earlier, whether or not related to Merck product, must be reported within 1 working day to the DFCI Coordinating Center (see Appendix C DFCI Reportable AE Coversheet) and Overall PI and within 2 working days to Merck Global Safety.

Non-serious Events of Clinical Interest will be forwarded to Merck Global Safety and will be handled in the same manner as SAEs.

Additionally, any serious adverse event, considered by an investigator who is a qualified physician to be related to Merck product that is brought to the attention of the investigator at any time outside of the time period specified in the previous paragraph also must be reported immediately to the DFCI Coordinating Center, Overall PI and to Merck.

SAE reports and any other relevant safety information are to be forwarded to the Merck Global Safety [contact]

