A copy of all 15 Day Reports and Annual Progress Reports is submitted as required by FDA, European Union (EU), Pharmaceutical and Medical Devices agency (PMDA) or other local regulators. Investigators will cross reference this submission according to local regulations to the Merck Investigational Compound Number (IND, CSA, etc.) at the time of submission. Additionally investigators will submit a copy of these reports to Merck & Co., Inc. (Attn: Worldwide Product Safety; [contact]) at the time of submission to FDA.

All subjects with serious adverse events must be followed up for outcome.

Investigators **must** report to the Overall PI any serious adverse event (SAE) that occurs after the initial dose of study treatment, during treatment, or within 90 days of the last dose of treatment (or the initiation of new anti-cancer therapy, whichever is earlier) on the local institutional SAE form.

For multi-institution studies where a DF/HCC investigator is serving as the Overall Principal Investigator, each participating institution **must** abide by the reporting requirements set by the DF/HCC. This applies to any medical event equivalent to an unexpected grade 2 or 3 with a possible, probable or definite attribution, unexpected grade 4 toxicities, and grade 5 (death) regardless of study phase or attribution.

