12.2.5.2 Safety Analysis Populations

The All Patients as Treated (APaT) population will be used for the analysis of safety data in this study. The APaT population consists of all allocated subjects who received at least one dose of study treatment.

At least one laboratory or vital sign measurement obtained subsequent to at least one dose of study treatment is required for inclusion in the analysis of each specific parameter. To assess change from baseline, a baseline measurement is also required.

Details on the approach to handling missing data for safety analyses are provided in Section 12.2.6 Statistical Methods.

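### The plan contradicts itself on when safety counting starts, and its dosed-patients-only safety set treats the two randomised groups unequally around surgery

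*Combined protocol and SAP*

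**What the plan says.** Safety is a primary objective for both stages (Section 1.2.3). Section 2.3.3.2 describes it as characterising tolerability both before and after surgery. The Stage 1 groups differ by one pembrolizumab infusion, given to Group A only, 14 ± 5 days before resection. Group B's first dose comes after recovery, no later than 35 days after surgery (Section 5.3; Section 9, footnote x).

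The documents give three different starting points for safety:

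- **First dose.** Section 10.1, item 10.1.1, says that participants given at least one dose "will be evaluable for toxicity from the time of their first treatment". One paragraph of Section 6.3.1 requires reporting to the Overall PI of "any serious adverse event (SAE) that occurs after the initial dose of study treatment". Section 6.3.2 also starts events of clinical interest at first dose.
- **Registration.** Section 5 says, in the same words for Group A, Group B and the Stage 2 expansion: "The toxicity evaluation period will begin with registration and extend to 30 days after last treatment day". Section 6: "All adverse events will be recorded from registration through 30 days following cessation of treatment". Section 9, footnote p: "adverse events experienced by participants will be collected and recorded from registration to the 30-Day Post Drug Visit".
- **Consent.** Another paragraph of Section 6.3.1 takes SAEs "from the time the consent is signed through 90 days following cessation of treatment".

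On who is analysed, Section 12.1.2 makes anyone given any pembrolizumab evaluable for toxicity, and Section 12.2.5.2 states: "The APaT population consists of all allocated subjects who received at least one dose of study treatment". Neither section gives a date from which events count. Section 12.2.6.2 promises descriptive summaries for both cohorts and is also silent on the window. An intention-to-treat set appears only under efficacy (Section 12.2.5.1).

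**The concern.** Stage 1 is the only part of the trial with a randomised comparison, and the randomised difference is a dose given shortly before a craniotomy. Readers of the by-group safety tables will look there for any sign that this dose adds perioperative harm. Two features of the plan could distort that picture.

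First, the start of the window is not settled. An analyst who follows Section 10.1 would leave out Group B's pre-surgical and perioperative events and keep Group A's. An analyst who follows Section 5 would keep both. The SAP does not choose between them.

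Second, entry to the safety set depends on something that happens after randomisation, and depends on it differently in each arm. A Group A patient enters with the pre-surgical infusion. A Group B patient enters only if fit enough after surgery to be dosed. The Group B patients most likely to be missing are those with serious surgical complications.

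Both features lower Group B's apparent event rate relative to Group A's, so they push the comparison in the same direction: against the pre-surgical dose.

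**Working it through.** The documents state no safety sample size, perioperative event rate or safety power, so there is no planned figure to reproduce.

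**1. The window under a literal reading of Section 10.1**

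Inputs: Group A dosed 14 ± 5 days before surgery, so 9 to 19 days; Group B's first dose up to 35 days after surgery.

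Days counted in Group A but not in Group B = days from Group A's dose to surgery + days from surgery to Group B's first dose, taking the latest permitted Group B start:

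- shortest lead: 9 + 35 = 44 days
- nominal lead: 14 + 35 = 49 days
- longest lead: 19 + 35 = 54 days

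A Group B patient who starts earlier than day 35 shortens the gap by the same number of days.

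**2. The window under Section 5, Section 6 and the calendar**

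Both groups count from registration, and the gap in step 1 disappears. The size of this first problem therefore depends entirely on which passage the analyst follows.

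**3. What the dosed-only safety set does even with a registration start**

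Let p be the true proportion with a perioperative event, equal in both groups. Let q be the share of Group B patients with such an event who never start pembrolizumab. Assume that Group B patients without an event all start. Neither p nor q is in the documents; both are assumptions.

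- Proportion of Group B remaining in the safety set: 1 − pq
- Proportion of Group B with an event and still in the set: p(1 − q)
- Group B's apparent rate: p(1 − q) / (1 − pq)

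Group A's apparent rate stays at p, because its patients enter before surgery.

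| p | q | Calculation | Group B apparent rate | Expected Group B patients lost, of 15 |
|---|---|---|---|---|
| 30% | 10% | 0.270 / 0.970 | 27.8% | 0.45 |
| 30% | 25% | 0.225 / 0.925 | 24.3% | 1.1 |
| 30% | 50% | 0.150 / 0.850 | 17.6% | 2.25 |
| 20% | 10% | 0.180 / 0.980 | 18.4% | 0.3 |
| 20% | 25% | 0.150 / 0.950 | 15.8% | 0.75 |
| 20% | 50% | 0.100 / 0.900 | 11.1% | 1.5 |

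With identical true risk, the tables would show a spurious excess in Group A of 2.2 to 12.4 percentage points at p = 30%, and 1.6 to 8.9 points at p = 20%. The patients behind that excess number between a fraction of one and about two out of 15.

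**The case against.** A reader of Section 10.1 alone might infer that toxicity is counted only from the first dose, and that the trial has lost its randomised control for perioperative safety. The documents do not support that. Section 5 starts the toxicity evaluation period at registration for Group B in terms, Section 6 and the calendar record events from registration, and SAEs are taken from consent. The control-group data are collected. Item 10.1.1 is a single line among the anti-tumour effect definitions, outside the SAP, and the SAP's silence does not adopt it.

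It can also be said that Group B was designed as a control for the pharmacodynamic endpoints (Sections 5 and 12.2.3), not for safety. The safety objective concerns patients who received drug, and Section 12.2.6.2 is descriptive. This stands to the extent that no between-group safety test is planned, so significance calculations on perioperative counts would illustrate an analysis that the plan does not contain. It does not dispose of the point, because cohort summaries set side by side will be compared whether or not a test is attached.

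The two SAE paragraphs are mainly a wording conflict. A site that follows both still reports from consent, and no loss of data is shown.

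None of these arguments answers the unequal entry to the safety set. A registration start does not cure it, and no other section does.

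**Conclusion.** The point holds in two parts. The start of the safety window is contradictory across Sections 5, 6, 6.3.1, 6.3.2, 9 and 10.1, and the SAP does not resolve it. If Section 10.1 were followed literally, up to 44 to 54 days around surgery would count in Group A only. If Section 5 were followed, no such gap would arise.

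Independently of the window, requiring at least one dose drops undosed Group B patients and keeps their Group A counterparts. At an assumed true rate of 30%, Group B would appear as 27.8%, 24.3% or 17.6% for non-start shares of 10%, 25% or 50%. These figures rest on assumed rates and on unaffected Group B patients all starting drug. If unaffected patients failed to start equally often, the bias would vanish. The direction is the more secure conclusion, provided that a surgical complication makes starting drug less likely.

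The randomised contrast exists in Stage 1 only, since Stage 2 enrols Group A alone. The matter should be corrected because safety is a primary objective and the correction is cheap.

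**What to change.** 1. Reconcile item 10.1.1, the first-dose SAE paragraph in Section 6.3.1 and the first-dose window in Section 6.3.2 with Section 5, Section 6, the consent-based SAE paragraph in Section 6.3.1 and calendar footnote p.
2. State in Section 12.2.6.2 that events are counted from registration in both groups.
3. Add a descriptive by-arm table of AEs and SAEs for all randomised Stage 1 patients as assigned, from registration to the first post-operative dose, or to day 35 after surgery if no dose is given. Show Stage 2 Group A separately. State the cut-off for anyone who does not reach surgery.
4. Keep the All Patients as Treated set for toxicity under drug exposure.

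The cost is one extra table, built from data that the plan already records from registration. Its drawback is that it includes events in patients not yet exposed to drug, so it should be labelled as a perioperative summary and not as drug toxicity. One check is needed. Section 4.1 takes participants who receive no protocol therapy off study, and the recording window ends relative to stopping treatment, which is undefined for someone never dosed. The sponsor should confirm how far events were recorded in those patients and report their number by arm. No clinical procedure changes.
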